An implantable gastric stimulator (gastric pacemaker) has been used to treat obesity; this achieves excess weight loss up to 40% in approximately 1 year. The stimulator can be placed laparoscopically or endoscopically, but is invasive (1-3). The modulation of neuronal activities and release of certain hormones with an implantable gastric stimulator may explain the reduction of appetite and the increase of satiety, such as a decrease in ghrelin levels (4).

[figure not shown]
Viscerovisceral spinal sympathetic reflexes appear to play an important role in the autonomic control of thoracoabdominal viscera, such as the heart and great vessels (5). However, somatic stimulation may also affect visceral function through autonomic reflexes. The best known somatovisceral response is the effect of cold pain on vasomotor reactions (6). Evidence suggests that the gastrointestinal tract may also be influenced by such somatovisceral reflexes; thus, in anesthetized rats, cutaneous stimuli applied to the abdomen and hind paw decrease and increase stomach motility, respectively. Whereas the latter reflex response appears to relay centrally and the efferent limb of the reflex is located in vagal fibers, the response to abdominal stimulation involves a somatosympathetic reflex that relays at the level of the spinal cord, being retained in cervical cord-transected rats (7).

In studies performed by the Principal Investigator 30 years ago (8), sustained somatic stimulation by transcutaneous electrical nerve stimulation (TENS) was applied to the skin of human volunteers while simultaneously monitoring their upper gastrointestinal phasic pressure activity, extraintestinal vasomotor indices, and plasma levels of putative humoral mediators of autonomic reflexes (Figure 1). Figure 1.

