Stimuli were applied either to the hand (C8-T1) or to the upper abdomen (T5-T10) to determine whether impulses at these two dermatomes produced different effects on fed antral phasic pressure activity. TENS resulted in significant reduction (p=0.007) in antral motility index when applied to the hand and abdomen, as compared with sham stimulation (Figure 2). This was associated with increases in skin conductance and plasma beta-endorphin levels, but there were no changes in pulse, blood pressure, or circulating catecholamine levels. No qualitative changes in proximal intestinal pressure activity were detected. These studies suggested that sustained somatic stimuli resulted in reduced postprandial antral phasic pressure activity and the similarity in the responses to TENS applied to the hand and abdominal dermatomes suggests that the somatovisceral responses may relay at the central level.

Figure 2.

While effects of TENS dermatomal stimulation on gastric emptying was not evaluated in the earlier studies, more recent data suggested that cutaneous gastric electrical stimulation slowed gastric emptying (9). Furthermore, Electrical stimulation of the dorsal columns of the spinal cord to prevent the perception of intractable neuropathic pain signals in two patients was associated with appetite reduction and weight loss (10). In a large study, Ruiz-Tovar et al. showed that percutaneous electrical neurostimulation of dermatome T6 was associated with appetite reduction than diet alone in morbidly obese patients (11).

Figure 3 shows effects on pre-treatment and post-treatment appetite scores and proportion with weight loss >5kg (11).

[figure not shown]
Figure 3.

[figure not shown]
T6 stim active Diet alone

T6 stim active Diet alone

Proportion with weight loss >5kg

Appetite score (0-10 VAS)

The effects of T6 dermatomal electrical stimulation on gastric motor functions in otherwise healthy overweight or class I obese volunteers are unclear.

HYPOTHESIS AND SPECIFIC AIM

Hypothesis

T6 dermatomal electrical stimulation results in delay of gastric emptying of solids, reduction in gastric volume, inhibition of appetite, and weight loss in healthy volunteers who are overweight or have class I obesity.

Aim

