T6 dermatomal stimulation will be achieved by utilizing an Elira TENS device (Elira Therapeutics, Inc., St. Louis, MO), following the company's protocol. The Elira device provides a broad range of options for stimulation parameters. In particular, pulse width is programmable from 25 μ sec to 400 μ sec, pulse amplitude from 1 mA to 45 mA, pulse frequency from 1 Hz to 200 Hz, session duration from 5 min to 60 min, and number of sessions per day from 0 to 8 sessions.

- Participants will undergo four stimulation sessions per day (daily for at least 3 months) distributed around 2 meals (breakfast and dinner) as follows: A 15-minute pre-prandial session (starting 15 minutes before the meal) and a 60-minute post-prandial session (starting immediately after the meal), during which the participant can walk around and continue to perform regular activities as desired, with the exception of driving and operating machinery
- The stimulation parameters will be: 200 µsec pulse width at 20 Hz with a goal amplitude range of 18-20 mA (depending on the subject's pain threshold). Participants will be instructed to begin each stimulation at 0 mA and increase as tolerated (within 5 minutes) to achieve the 18-20 mA goal.

Clinical trial stimulation will be limited to an accumulated maximum of 150 Joules per day, with a maximum of 0.001 Joules (1 mJ) per pulse. For example, two 15-minute and two 60-minute stimulation sessions at 200 µsec pulse width, 20 Hz and 25 mA deliver an accumulated 40.5 Joules per day, with only 0.23 mJ per pulse, allowing for upward titration as needed. The principal investigator may increase or decrease any of the stimulation parameters at his discretion up to the maximum 150 Joules daily limit.

Blood Samples

[figure not shown]
Fasting, 15, 45, and 90 minute post-prandial blood samples will be collected at the baseline and treatment conclusion visits, and will be stored at -70°C for assay analysis of plasma gastrointestinal hormone levels as well as storing a blood-based DNA sample for possible future genetic testing. Fasting blood glucose will be measured at one of the baseline visits using a glucometer (CRTU nurses).

Quantitative Traits

On different days, participants will attend Mayo Clinic Clinical Research Trials Unit at a prescheduled time after an 8-hour fasting period, and the following validated quantitative traits will be measured.

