Yes, very much	Would you like to eat something sweet?	No, not at all	average of the four individual scores (satiety + fullness + 100-prospective food consumption + 100-hunger / 4.	
Yes, very much	Would you like to eat something salty?	No, not at all	6. Plasma gastrointestinal hormones (ghrelin, GLP-1 and PYY) by radioimmunoassay measured	
Yes, very much Yes, very much	Would you like to eat something savoury?	No, not at all	at fasting, and 15, 45, and 90 minutes	
	Would you like to eat something fatty?	No. not at all		

postprandially during the NDT. The primary endpoint is the peak postprandial level. CCK levels will not be measured in the current study, since they were non-informative in our prior studies. Total ghrelin will be measured by a radioimmunoassay technique (Linco Research, Inc., St. Charles, MO). The assay uses ¹²⁵I-labeled ghrelin and a ghrelin antiserum to determine the level of total ghrelin in plasma.GLP-1 will be measured as the biologically active GLP-1 (active and total) using a 2-site non-competitive immunoassay based on enzyme-labeled quantification of GLP-1 detected by a fluorogenic substrate. PYY will be measured by radioimmunoassay (Linco Research, Inc., St. Charles, MO). PYY exists in at least 2 molecular forms, 1-36 and 3-36, both of which are physiologically active and are detected by the assay.

7. Self-administered questionnaires assessing affect, exercise performance, attitudes, satisfaction with body image, and eating behavior (12-14,23-26).

Statistical Analysis

Sample size assessment - Sample size assessment is based on the results of primary endpoints in the Mayo Clinic lab. Assuming the intra-individual coefficient of variation (or standard deviation) is similar to the inter-individual variation, we have used the SD_{inter} for estimating the power of the study (n=16, baseline versus post-treatment).

Response	Mean	SD	Predicted detectable effect size (%(absolute #)), n=16 on treatment compared to baseline, paired analysis
Gastric emptying, T _{1/2} min*	121.7	29.8	18.4% (22.4 min)
Fasting gastric volume, ml**	225	65	21.8% (49mL)
Gastric accommodation, ml**	507	100	14.7% (75mL)

Data obtained from *ref. 16 and **ref. 20; predicted detectable effect size is shown with 80% power, α =0.05.

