The sample size of 16 on-treatment relative to baseline will have sufficient power to detect a difference in gastric emptying of 22.4 min, of fasting gastric volume of 49mL, and in gastric accommodation of 75mL.

Statistical Methods

It is anticipated that all primary and secondary endpoints will be normally distributed. We shall use a paired student's t-test to compare study parameters (differences between baseline and on-treatment). An analysis of covariance may be examined using gender and BMI as covariates, since these may significantly affect gastric functions such as satiation, maximum tolerated volume, and gastric emptying.

Interim Analysis

An administrative interim analysis will be completed after 6 subjects have completed at least 4 weeks of treatment. The data will be submitted in a blinded fashion to the study sponsor's statistician while the investigative team remains blinded to the treatments. This interim analysis will be conducted for administrative purposes to provide information about future planning of other research activities. The

conduct of this study will not be altered and all planned research activities will proceed until the completion of the targeted 16 subjects.

Primary endpoints

- 1. Body weight change from baseline
- 2. Gastric emptying $T_{1/2}$ after day 1 treatment
- 3. Gastric emptying $T_{1/2}$ after 3 months treatment

Secondary endpoints

- 1. Fasting gastric volume
- 2. Postprandial gastric volume or accommodation volume
- 3. Gastric emptying % at 1 hour in day 1 and end of three months of treatment
- 4. Satiation: volume to fullness (grade 3) and maximum tolerated volume (grade 5)
- 5. Satiety: kcal intake at buffet meal
- 6. Appetite score during satiety meal test and at weekly intervals (at home)
- 7. Plasma ghrelin, GLP-1 and PYY fasting
- 8. Peak postprandial plasma ghrelin, GLP-1 and PYY fasting

Anticipated Results and Significance

We anticipate greater weight loss with active treatment with dermatomal stimulation compared to baseline. The sample size is not sufficient to appraise twice versus once daily treatment. However, the data will be tabulated for descriptive analysis. The physiological measurements will provide information about the potential mechanisms involved in any beneficial effects on weight and appetite.

Potential Pitfalls, Precautions Taken, and Alternative Strategies

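### Postprandial ghrelin is summarised by its peak, which can miss a fall that comes mainly after the 15 minute sample

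*Combined protocol and SAP*

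**What the plan says.** Quantitative Traits, item 6, treats ghrelin, GLP-1 and PYY together and gives them one summary: "The primary endpoint is the peak postprandial level". Secondary endpoint 8 repeats it with ghrelin named: "Peak postprandial plasma ghrelin, GLP-1 and PYY fasting". Secondary endpoint 7 lists the fasting levels separately: "Plasma ghrelin, GLP-1 and PYY fasting".

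The sampling is set under Blood Samples: "Fasting, 15, 45, and 90 minute post-prandial blood samples will be collected at the baseline and treatment conclusion visits". The postprandial peak is therefore the maximum of three values. Neither the lowest value, an AUC nor a change from fasting is defined for any hormone.

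The only direction given for ghrelin is in the Background, which discusses how an implantable gastric stimulator may work, "such as a decrease in ghrelin levels". The trial's own hypothesis names no hormone: "T6 dermatomal electrical stimulation results in delay of gastric emptying of solids, reduction in gastric volume, inhibition of appetite, and weight loss". The role of these measurements is stated under Anticipated Results and Significance: "The physiological measurements will provide information about the potential mechanisms involved in any beneficial effects on weight and appetite".

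**The concern.** The maximum of several samples is, by construction, the least suppressed one. That suits a hormone expected to rise after a meal. For a hormone whose change of interest is downward, it looks at the wrong end of the curve. If ghrelin falls after the meal, its peak will usually be the earliest sample, and a deeper fall later on barely moves it.

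At stake is the mechanistic reading. A real postprandial fall in ghrelin could be reported as no change, and the planning of the later hypothesis-testing trial could take that as evidence against a ghrelin effect.

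**Working it through.** **1. The plan's own figures.** With n=16, a paired t-test, two-sided α=0.05 (sidedness is not stated) and 80% power, the detectable difference is 0.749 times the SD of the paired difference. Using the SDs in the sample size table:
- gastric emptying T1/2: 0.749 × 29.8 = 22.3 min (stated 22.4)
- fasting gastric volume: 0.749 × 65 = 48.7 mL (stated 49)
- accommodation: 0.749 × 100 = 74.9 mL (stated 75)

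The figures reproduce. None is for a hormone, so this point changes none of them.

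**2. Assumptions for ghrelin.** The documents give no ghrelin mean, SD, time course or expected effect, so all of these are assumed. Mean levels are 100 fasting, then 95, 80 and 70 at 15, 45 and 90 minutes. Each sample has a within-person SD of 10 (range 5 to 15), independent between samples and visits except in step 5. Each scenario is 20,000 simulated trials with n=16 and a paired t-test.

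**3. Which sample is the peak?** Two samples in one visit differ with SD √2 × 10 = 14.1. The 45 minute value exceeds the 15 minute value with probability 1 − Φ(15/14.1) = 0.14. For the 90 minute value it is 1 − Φ(25/14.1) = 0.04. So the peak is the 15 minute sample in at least 1 − 0.14 − 0.04 = 82% of visits.

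**4. Power by shape of effect.**

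| Fall at 15/45/90 min | Peak, SD 5 / 10 / 15 | Lowest value, SD 5 / 10 / 15 | AUC 0-90, SD 10 |
|---|---|---|---|
| 0/10/10 | 5% / 6% / 7% | 100% / 86% / 54% | 89% |
| 3/7/10 | 36% / 18% / 14% | 100% / 80% / 47% | 84% |
| 10/10/10 | 100% / 84% / 57% | 100% / 86% / 58% | over 99% |

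Repeat runs differ by up to about one percentage point. With no effect, the summaries reject in about 5% of trials.

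**5. Correlated samples.** The trapezoid weights for the time-averaged AUC are 7.5, 22.5, 37.5 and 22.5, each over 90. In the first row of the table the AUC falls by 10 × (37.5 + 22.5)/90 = 6.67. The sum of squared weights is 2475/8100 = 0.306. With within-visit correlation ρ, the variance at one visit is 100 × [ρ + (1 − ρ) × 0.306], and the paired difference has twice that variance.
- ρ=0: SD of the difference 7.82, ratio 6.67/7.82 = 0.85, power 89%
- ρ=0.5: SD 11.43, ratio 0.58, power about 59%
- ρ=0.8: SD 13.12, ratio 0.51, power about 47%

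The benchmark for 80% power is the 0.749 of step 1. In the same scenario the lowest value keeps 75% to 79% for ρ of 0.5 to 0.8, and the peak stays near 5%.

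**6. Does fasting ghrelin fill the gap?** If the fall is 10 at all four times, the fasting ratio is 10/14.1 = 0.71 and power is 75%. If the effect is postprandial only, fasting ghrelin rejects at about 5%, the error rate.

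**The case against.** The case on the other side is substantial, and much of it stands.

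- A reader might infer that a fall in ghrelin is the plan's own mechanism for T6 stimulation. The documents do not support that. The Background remark concerns a different, implanted device and is tentative, and the trial's hypothesis names no hormone.
- Fasting ghrelin is tested separately. A general fall, which is all the Background describes, could show there and would lower the peak too. This stands for a general fall, but not for a purely postprandial one (step 6).
- The size of the loss is set by the assumed shape. With a uniform fall, peak and lowest value are nearly equal. The converse also holds: a fall confined to the 15 minute sample would move the peak and leave the lowest value almost untouched. The documents do not say which shape to expect.
- The AUC's apparent advantage relies on independent errors (step 5). This stands, and is why the AUC is better as support than as the main summary.
- The word primary in item 6 means the main readout of that assay; item 1 uses it in the same way for gastric emptying. A reader might take it as a primary endpoint of the trial, but the Secondary endpoints list places it last of eight, and Potential Pitfalls (b) calls the study a hypothesis-generating pilot.
- Potential Pitfalls (c) allows exploratory analyses of the other traits, so postprandial ghrelin could be looked at again. No summary is named there, so the choice would be made after the data are seen.

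**Conclusion.** The point holds in a limited form, and its severity is minor. The plan applies a maximum to ghrelin by name, while the only direction it mentions for ghrelin is a decrease. If ghrelin falls after the meal, the peak can miss a treatment effect that is confined to, or larger at, 45 and 90 minutes, and the fasting endpoint does not cover a purely postprandial effect.

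At SD 10 the assumed loss runs from very large (6% against 86%) through large (18% against 80%) to almost nothing (84% against 86%). A reader might carry away the first pair as the size of the problem. The documents do not support that, because they give no ghrelin time course, SD or effect shape. What can be said is that, across the three shapes in the table, the lowest value does as well as or better than the peak, up to simulation error.

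No primary endpoint, stated power figure or trial decision is affected. The consequence is confined to how one secondary endpoint is read as evidence on mechanism.

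**What to change.** In Quantitative Traits item 6 and in secondary endpoint 8, define the ghrelin endpoint as the lowest of the 15, 45 and 90 minute levels. Add AUC 0-90 minutes, by the trapezoid rule from the four samples, as a supporting summary. Keep the peak for GLP-1 and PYY, and keep fasting ghrelin as secondary endpoint 7.

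While rewording item 8, remove its closing word, fasting, which conflicts with a postprandial peak and repeats item 7. This is editorial and adds no weight to the point.

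The cost is wording only: the samples and assays stay the same. The change should be fixed before the hormone results are seen.

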In 16 participants with BMI 25-34.99 kg/m², treated before and after two meals of the day with T6 dermatomal electrical stimulation (delivered by a TENS unit), we aim to compare baseline measurements of gastric emptying of solids with measurements on day 1 of treatment and after 4 weeks and 3 months of treatment. We also aim to compare baseline measurements of fasting and postprandial gastric volume, satiation, satiety, appetite, and weight with measurements after three months of treatment.

EXPERIMENTAL DESIGN

Overweight or class I obesity participants who are not on metformin and have not been diagnosed with type 2 diabetes mellitus (other than dietary advice for borderline hyperglycemia) will be recruited for the study.

Participants will undergo baseline measurements of height, weight, BMI, pulse, blood pressure, gastric function, satiation, satiety, and incretin hormones, over a period of 3 to 7 days. In an open-label study, all 16 participants will receive 15-minute T6 dermatome cutaneous stimulations with a TENS unit applied immediately before ingestion of two of the main meals of the day (breakfast and evening meal), and 60-minute stimulations applied immediately after ingestion of these meals.

[figure not shown]
Participants will attend the Mayo Clinic Clinical Research Trials Unit during the first day of treatment, within 2 weeks from completion of baseline testing. During this visit (day 1 of treatment), devices will be provided and participants will receive training on self-administering electrical stimulation. Hence, the first set of electrical stimulations will take place at Mayo Clinic. On this day, participants will also undergo a gastric emptying test as a measure of the acute effect of T6 dermatome cutaneous stimulation on gastric emptying.

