Participants will apply the stimulus four times daily for a treatment period of at least 3 months, at the time of breakfast and evening meals (starting 15 minutes preprandially and immediately postprandially for 60 minutes). After 4 weeks of treatment, the participants will be asked to return to the Clinical Research and Trials Unit for a repeat of the gastric emptying study identical to the procedure performed at baseline. During the three-month treatment period, participants will keep a diary of weight, measured on the same weighing scales in their homes once weekly, and a weekly appetite record (0-10cm VAS, paper diary). The stimulation parameters will be: 200 µsec pulse width at 20 Hz with a goal amplitude range of 18-20 mA. Each stimulation will begin at 0 mA and increase quickly to achieve the 18-20 mA dose. Clinical trial stimulation will be limited to an accumulated maximum of 150 Joules each day; For example, two 15-minute and two 60-minute stimulation sessions at 200 µsec pulse width, 20 Hz and 25 mA deliver an accumulated 40.5 Joules per day. Participants that do not tolerate the discomfort or develop nausea likely caused by the TENS unit, will report to the investigational team thepost-prandial duration of stimulation may be reduced from the targeted duration of 60 minutes postprandially).

During the final week of the three-month treatment period or at the time of early withdrawal, participants will undergo the same measurements as performed during the previous gastric emptying test days. During these studies, participants will receive 15-minute T6 dermatome cutaneous stimulations with the TENS unit immediately before meal ingestion and 60-minute stimulations immediately after meal ingestion, in the different tests.

Figure 4 is a schematic that summarizes the main events that will take place in this study.

Figure 4.

METHODS

Participants

Overweight or class I obese participants who are not on metformin and have not been diagnosed with type 2 diabetes mellitus (other than dietary advice for borderline hyperglycemia) will be recruited for the study. The objective is to have 16 participants complete all investigative testing over approximately 14 weeks. Therefore, we may screen and enroll up to 36 participants in order to ensure 16 fulfill eligibility criteria and complete the study.

Inclusion Criteria

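### Does the interim text's claim of a blinded team in an open-label, one-treatment study, with no statement on masked scan processing, require a change?

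*Combined protocol and SAP*

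**What the plan says.** The Interim Analysis section plans one administrative look after 6 participants have had at least 4 weeks of treatment. On masking it says: "The data will be submitted in a blinded fashion to the study sponsor's statistician while the investigative team remains blinded to the treatments". It adds that the look serves planning of other research and that the study will run to 16 participants regardless.

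Experimental Design says: "In an open-label study, all 16 participants will receive 15-minute T6 dermatome cutaneous stimulations with a TENS unit". Of the first treatment day, at the study unit, it says: "devices will be provided and participants will receive training on self-administering electrical stimulation". Everyone follows one schedule: "Participants will apply the stimulus four times daily for a treatment period of at least 3 months". Under T6 Dermatomal Stimulation, the principal investigator may adjust the stimulation parameters within a daily limit. Anticipated Results and Significance nevertheless remarks that the sample is too small to compare once-daily with twice-daily treatment.

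For the scans, the Aim in the Research Plan is to "compare baseline measurements of gastric emptying of solids with measurements on day 1 of treatment and after 4 weeks and 3 months". For gastric volume and the other measures it says: "We also aim to compare baseline measurements of fasting and postprandial gastric volume, satiation, satiety, appetite, and weight with measurements after three months". Quantitative Traits gives scan times, endpoints and the validation of SPECT. It does not say who processes the images or whether that person knows the visit.

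**The concern.** With one known treatment, a team that issues the devices, trains the participants and can change the settings cannot be blinded to treatment. A reader who took the interim sentence at face value would credit the study with a protection that it lacks.

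The question with possible consequences is image processing. The analysis is a paired comparison of baseline with on-treatment values, so knowing the visit means knowing the exposure. The hypothesis has a direction: "T6 dermatomal electrical stimulation results in delay of gastric emptying of solids, reduction in gastric volume, inhibition of appetite, and weight loss". The closing tests are also easy to recognise: "During the final week of the three-month treatment period or at the time of early withdrawal, participants will undergo the same measurements", with the stimulator in use around the test meals. If an operator's judgement enters the half-emptying time or the gastric volume, a known visit could push results the expected way. Without a control arm, masked processing is one of the few safeguards still available.

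**Working it through.** **1. The plan's own figures.** Inputs from the sample size table: n = 16, two-sided alpha 0.05 (sidedness is not stated, but two-sided reproduces the table), and the tabulated SD used as the SD of the paired difference. Power comes from the noncentral t distribution with 15 degrees of freedom and noncentrality d × √16 / SD.

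| Measure | SD | Stated difference d | Noncentrality 4d/SD | Power at d | Difference at 80% power |
|---|---|---|---|---|---|
| Half-emptying time | 29.8 min | 22.4 min | 3.007 | 0.8023 | 22.33 min |
| Fasting volume | 65 mL | 49 mL | 3.015 | 0.8045 | 48.72 mL |
| Accommodation | 100 mL | 75 mL | 3.000 | 0.8006 | 74.95 mL |

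The table reproduces. The blinding sentence enters none of these inputs.

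**2. The interim sentence against the design.** Experimental Design gives one open-label treatment to all, while Interim Analysis gives a team blinded to treatments. Both cannot be true, and the detailed design text leaves no doubt which describes the study. Sending data in a blinded fashion to the sponsor's statistician can still make sense in one arm if it means de-identified or visit-coded data; the plan does not say which. The look has no stopping or adaptation rule, so the final test keeps its alpha of 0.05.

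**3. The once-versus-twice-daily remark.** It matches no allocation in the plan. T6 Dermatomal Stimulation lists sessions per day among the programmable options and lets the principal investigator vary parameters, so the remark may refer to stimulation as actually used, tabulated descriptively. The wording does not settle this, and no planned test depends on it.

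**4. Reach of the scan question.** Each completer has 4 emptying studies (baseline, day 1, 4 weeks, 3 months) and 2 SPECT studies (baseline, 3 months). That gives 16 × 4 = 64 and 16 × 2 = 32, or 96 in all. Scan-derived measures are primary endpoints 2 and 3 of 3, and items 1 to 3 of the 8 listed secondary endpoints. Quantitative Traits adds the proportions emptied at 2 and 4 hours.

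**5. What a reading bias would do, if there were one.** The documents give no value, so these shifts are assumed. With no true effect, SD of the difference 29.8 min and n = 16, the noncentrality is 4 × shift / 29.8.

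| Assumed shift in half-emptying time | Noncentrality | Two-sided false-positive rate |
|---|---|---|
| 0 min | 0 | 5% |
| 2 min | 0.268 | 5.7% |
| 5 min | 0.671 | 9.6% |
| 10 min | 1.342 | 24.2% |

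The result runs from no effect to a material one, and nothing in the plan says where in that range the study lies.

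**The case for a change.** The best argument for a change is that masking costs little. Coded labels on about 96 image studies need no extra visit or procedure, and the smallest worrying shifts are well inside the 22.4 min detectable difference (10 / 22.4 = 45%). The study names primary endpoints and a formal test, so calling it a pilot does not excuse avoidable bias.

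Part of this stands. The plan is silent, the visit is the exposure, and a sentence on laboratory practice would help a reader. But silence is not evidence of unmasked reading. Quantitative Traits relies on established laboratory methods and cites their validation, and no section says that staff who attend the visit also process the images. A request to state existing practice differs from showing that a planned rule gives a wrong answer.

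The gain would also be narrow. Masked processing does nothing for body weight, the remaining primary endpoint, or for self-rated appetite. Nor does it separate stimulation from the recommended 1200 or 1400 kcal diet, or from time, in an uncontrolled before-after comparison. The Potential Pitfalls section itself calls the study hypothesis-generating. Deleting the interim clause also has a drawback: it may have been meant to keep interim results from the investigators, and deletion alone would leave unsaid who sees them.

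**Conclusion.** The contradiction is real but clerical. Experimental Design states plainly that the study is open-label with one treatment, and no analysis, alpha, power figure or decision depends on the interim sentence. The once-versus-twice-daily remark is a similar loose end. The sections can be reconciled as an editorial matter without touching the analysis.

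The silence on masked image processing is a gap in described practice, which the laboratory can fill sensibly. It bears on 2 of 3 primary endpoints and several secondary ones, but no bias is shown and none can be sized from the documents.

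This conclusion rests on two assumptions: that the interim look stays administrative, as written, and that images go through the laboratory's established procedure with little room for operator discretion. If the second failed, the effect could range as in the assumed-shift table, and it would belong among the limitations of an uncontrolled pilot when results are reported.
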